6.4.6.1.1. Sensitivity Analysis for Primary Efficacy Endpoints

In order to support the robustness of the conclusions drawn from the co-primary efficacy analyses, we will perform the following sensitivity analyses for the co-primary efficacy endpoints.

Percentage change in LDL-C from baseline to Day 510

- A control-based pattern-mixture model (PMM), using the same imputed datasets and MMRM model that was used for the second co-primary efficacy endpoint primary analysis will be used to compare treatments at Day 510. Multiple imputations will be used to account for uncertainty in the imputation process and results from the imputed datasets will be combined using Rubin’s method. (Refer to [Appendix 3](#) for details)
- A mixed model for repeated measurements (MMRM) analysis without multiple imputation, that assumes missing data are missing at random (MAR), will be performed. The model will include fixed effects for treatment, visit, baseline value, interaction

between treatment and visit, and current use of statins or other lipid-modifying therapies. The Restricted Maximum Likelihood (REML) estimation approach will be used with the covariance structure set as “Unstructured”. A linear contrast at Day 510 will be used to compare treatment groups. This will be the same model that is used as a sensitivity analysis for the second co-primary endpoint.

- The impact of country will be assessed by including country (possibly pooled into a region) and the treatment-by-country interaction fixed effects into the primary efficacy analysis ANCOVA (using multiple imputation washout model data).
- A tipping point analysis will be performed to search for the tipping point that reverses the study conclusion. In the tipping point analysis, we will independently vary the deltas in the treatment groups (inclisiran group progressively worse while the placebo group is not impacted and inclisiran group progressively worse while the placebo group progressively improves) until the hypothesis test on the co-primary efficacy endpoint becomes statistically insignificant. The MNAR(ADJUST) statement in SAS PROC MI will be used to adjust the delta of the imputed missing values analyzed using the ANCOVA model with washout model multiply imputed data.

Time adjusted percentage change in LDL-C from baseline after Day 90 and up to Day 540.

- A mixed model for repeated measurements (MMRM) analysis without multiple imputation, that assumes missing data are MAR, will be performed. The model will include fixed effects for treatment, visit, baseline value, interaction between treatment and visit, and current use of statins or other lipid-modifying therapies. The Restricted Maximum Likelihood (REML) estimation approach will be used with the covariance structure set as “Unstructured”. A linear combination of the estimated means after Day 90 and up to Day 540 will be used to compare treatment groups. This will be the same model that is used as a sensitivity analysis for the first co-primary endpoint.
- The impact of country will be assessed by including country (possibly pooled into a region) and the treatment-by-country interaction fixed effects into the primary efficacy analysis MMRM (using multiple imputation control-based PMM data).
- The time adjusted percentage change will also be calculated by taking the arithmetic mean of calculated percent change in LDL-C from baseline at each visit after Day 90 through Day 540. This analysis will be based on the control-based PMM imputed datasets (100 multiple imputation datasets). The two sample t-test will be performed to test the treatment difference between inclisiran and placebo. Results will be combined and summarized using Rubin’s method.
- A tipping point analysis will be performed to search for the tipping point that reverses the study conclusion. In the tipping point analysis, we will independently vary the deltas in the treatment groups (inclisiran group progressively worse while the placebo group is not impacted and inclisiran group progressively worse while the placebo group progressively improves) until the hypothesis test on the co-primary efficacy endpoint becomes statistically insignificant. The MNAR(ADJUST) statement in SAS PROC MI will be used to adjust the delta of the imputed missing values analyzed using the MMRM model with control-based PMM multiply imputed data.

Other sensitivity analysis may be performed.

6.4.6.2. Secondary Efficacy Endpoints

The secondary efficacy endpoints will not be tested if either one of the co-primary efficacy endpoints' null hypothesis fails to be rejected.

The key secondary endpoints of this study are:

- Absolute change in LDL-C from baseline to Day 510.
- Time adjusted absolute change in LDL-C from baseline after Day 90 and up to Day 540.
- Percentage change from baseline to Day 510 in PCSK9, total cholesterol, ApoB, and non-HDL-C.

The Hochberg procedure [[Hochberg, 1988](#)] will be applied to control the family-wise type I error rate at a two-sided significance level of $\alpha=0.05$ for the key secondary endpoints.

Missing values will be imputed using the control-based PMM (see [Appendix 2](#) for more details) on LDL-C, PCSK9, total cholesterol, ApoB, and non-HDL-C, absolute change or percent change from baseline will be calculated based on imputed data before any analysis is performed.

The absolute change in LDL-C from baseline to Day 510 and percentage change from baseline to Day 510 in PCSK9, total cholesterol, ApoB, and non-HDL-C will be analyzed using a MMRM with covariates as specified in Appendix 1 and Appendix 3. Time adjusted absolute change in LDL-C from baseline after Day 90 and up to Day 540 will be analyzed similarly to that of time adjusted percentage change in LDL-C from baseline after Day 90 and up to Day 540.

MMRM without multiple imputation (see [Appendix 1](#)) will be used as sensitivity analyses for the key secondary endpoints.

The other secondary endpoints of this study are:

- Maximum percentage change in LDL-C. This is calculated by finding the smallest LDL-C value across all post baseline visits for each individual subject. This value will be used to compare with each subject's baseline value and calculate the percent change from baseline to the lowest LDL-C value.
- Absolute change from baseline to Day 510 in PCSK9, total cholesterol, ApoB and non-HDL-C.
- Absolute change and percentage change in LDL-C from baseline to each assessment time up to Day 540.
- Individual responsiveness defined as the number of subjects reaching on treatment LDL C levels of <25 mg/dL, <50 mg/dL, <70 mg/dL, and <100 mg/dL at Day 510.
- Proportion of subjects in each group with greater or equal to 50% LDL-C reduction from baseline.
- Absolute change and percentage change in other lipids, lipoproteins, apolipoproteins, and PCSK9 from baseline at each subsequent visit to Day 540.

- Proportion of subjects in each group who attain global lipid targets for their level of ASCVD risk.

The two-sided 95% confidence interval for least squares means will be provided for continuous variables at a single point using an analysis of covariance model or using MMRM methods for variables measured over time (see [Appendix 1](#) for more details). The odds ratio and 95% confidence interval for the odds ratio will be provided for binary variables using logistic regression models. Nominal p-values will be provided when applicable.

Descriptive and graphical summaries by treatment group will also be presented.

6.4.6.3. Exploratory Endpoints

The exploratory endpoints of this study are:

- Incidence of CV death, resuscitated cardiac arrest, non-fatal MI, and stroke (ischemic and hemorrhagic)

A major cardiovascular event (MACE) is defined as the composite of CV death, resuscitated cardiac arrest, non-fatal MI, and stroke (ischemic or hemorrhagic). Refer to [Appendix 5](#) for details on the search terms used. The number and percentage of subjects with MACE or any of the individual events will be presented by treatment group.

- Proportion of subjects in each group with any LDL-C reduction from baseline at any visit (responders).

The number and percentage of subjects with any LDL-C reduction at any visit will be presented by treatment group. The odds ratio and 95% confidence interval for the odds ratio will be provided using a logistic regression model. The number and percentage of subjects with any LDL-C reduction will also be summarized at each visit.

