2.4. Schedule and Sequence of Procedures

The Schedule of Assessments (Table 1) summarizes the study assessments by time point.

This study consists of four periods: Screening, Randomization, Treatment, and End of Study.

- **Screening period (Days -14 to -1):** occurs prior to randomization and consists of confirming eligibility and collecting baseline assessments.
- **Randomization (Day 1):** occurs on the day of initial administration of investigational product.
- **Treatment period (Day 1 through Day 510):** occurs from the start of investigational product administration through the final clinic visit.
 - Dosing: Day 1, Day 90, Day 270, and Day 450 (final dose)
 - Additional clinic visits: Day 30, Day 150, Day 330, and Day 510
- **End of study (EOS) visit:** Day 540 (90 days past last dose)

For subjects who decided to prematurely and permanently discontinue from study treatment and who decline further follow-up visits, EOS visit will be scheduled as soon as possible. If decision to discontinue is made at a specific visit, this visit will become the EOS visit and EOS visit procedures should be followed.

The expected duration of the subjects' involvement in the study will be approximately 554 days which includes screening, investigational product administration, and the EOS period to Day 540.

Schedule of Assessments

Table 1: Study Design and Schedule of Assessments

Visits	Screening	Randomization	Treatment							EOS ¹
		V1 (baseline)	V2	V3	V4	V5	V6	V7	V8	V9 (90 days post last dose)
Timelines	Day -14 to -1	Day 1	Day 30	Day 90	Day 150	Day 270	Day 330	Day 450	Day 510	Day 540
Visit windows (± days)			±2	±30	±30	±30	±30	±30	±14	±14
Informed consent	X									
Assessment of eligibility	X	X ²								
Demographics and medical history	X									
Pregnancy test	X ³	X ³		X ³		X ³		X ³	X ³	X ³
Randomization		X								
Investigational product administration		X ^{4,5}		X ^{4,5}		X ^{4,5}		X ^{4,5}		
Physical examination	X									X
Neurological examination		X								X
Weight/height/waist circumference	X ⁶									X
Vital signs ⁷	X	X		X		X		X		X
12-lead ECG	X	X								X
Fasted lipid profile/biomarkers ⁸	X	X		X	X	X	X	X	X	X
ADA		X ⁹	X ⁹	X ⁹	X ⁹	X ⁹	X ⁹	X ⁹	X ⁹	X ⁹
Full Serum chemistry ¹⁰		X								X
Limited serum chemistry ¹⁰	X			X	X	X	X	X	X	
Urinalysis (local) ¹¹	X	X								X
Hematology and coagulation ¹²	X	X			X					X
Previous/concomitant medications	X	X	X	X	X	X	X	X	X	X
AEs/SAE reporting	X	X	X	X	X	X	X	X	X	X

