6. STATISTICAL PLAN

6.1. Sample Size

The sample size calculation is performed with the assumption (which is based on the observed results from a Phase II study) that the difference in change from baseline between the active dose group and the placebo group for LDL-C will be no less than 30 mg/dL, with a standard deviation of 20 mg/dL.

Assuming about a 5% drop out rate, the sample size will be approximately 1425 subjects that are evaluable for efficacy across the placebo and inclisiran dose groups. This sample size of at least 1425 evaluable subjects, will provide more than 90% power to detect a 30% reduction of LDL-C levels in the inclisiran group compared to the placebo group at one-sided significance level of 0.025. This sample size will also contribute additional sufficient safety data.

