6.3.3. Analysis Windows and Baseline

The analysis windows around each visit day are provided in [Table 2](#) below.

Table 2: Analysis Windows for Each Scheduled Visit

Scheduled Visit	Analysis Window	
	From	To
Baseline		Before randomization/First Study Treatment
Day 30	Day 1	Day 60
Day 90	Day 61	Day 120
Day 150	Day 121	Day 210
Day 270	Day 211	Day 300
Day 330	Day 301	Day 390
Day 450	Day 391	Day 480
Day 510	Day 481	Day 525
Day 540	Day 526	No upper limit

Data collected at scheduled or unscheduled visits will be used in the analysis if they fall into an analysis window for a scheduled visit. If more than one visit (scheduled or unscheduled) is made

within the window specified above for any scheduled visit, the non-missing assessment closest to the scheduled visit day will be used in the analysis for that visit. However, all data will be included in the subject data listings.

Unless otherwise specified, data collected from assessments that occur more than once prior to initiation of investigational product administration, the latest assessment will be considered the "Baseline" evaluation for analysis.

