6.3.4. Missing data handling

6.3.4.1 Efficacy

The sponsor will diligently follow up with each subject during the study through Day 540 \pm 14 days on all efficacy laboratory assessments of lipids/lipoproteins/biomarkers to keep missing data to a minimum regardless of whether the subject is on study treatment, uses ancillary therapies, experiences an adverse event, or adheres to the protocol (these data points are referred to as retrieved data). However, if missing data, defined as data not available from either scheduled (within the protocol defined visit window) or unscheduled visits, occurs for the primary or any of key secondary efficacy endpoints then that data will be imputed.

The primary method to impute missing data for the first co-primary efficacy endpoint (percentage change in LDL-C from baseline to Day 510) will be a multiple imputation washout model. The washout model will be performed on actual values, change and percentage change values are calculated after the imputation. All retrieved data for subjects who dropped out from study treatment are considered as non-missing data and will be utilized in all analyses. See [Appendix 2](#) for full details of the multiple imputation washout model.

In addition, sensitivity analyses using MMRM without multiple imputation and a control-based pattern mixture model (PMM, see details in [Appendix 3](#)) will be performed on the co-primary and key secondary efficacy endpoints to assess the impact of missing values. Note that the control-based PMM will be the primary method for imputing data for the second co-primary efficacy endpoint (time adjusted percentage change in LDL-C from baseline after Day 90 and up to Day 540).

Unless otherwise specified, missing data for all parameters not listed in the primary and key secondary endpoints will not be imputed and will be excluded from the associated analysis.

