APPENDIX 1. DETAILS OF MMRM USED FOR EFFICACY ANALYSES

A number of efficacy analyses will utilize a mixed-effects model for repeated measures (MMRM). This includes the co-primary efficacy endpoints (in the case of the first co-primary efficacy endpoint, it will be used as a sensitivity analysis), the key secondary efficacy endpoints, and other secondary efficacy endpoints.

The models will generally include fixed effects for treatment, visit, baseline value, interaction between treatment and visit, and current use of statins or other lipid-modifying therapies. The visits will include Days 90, 150, 270, 330, 450, and 510, with Day 510 as the primary time-point. Linear combinations of the estimated means will be created for the various hypothesis tests.

The Restricted Maximum Likelihood (REML) estimation approach will be used with the covariance structure set as “Unstructured.” The least squares means will be calculated for each treatment at each visit.

The analysis will be carried out using the SAS PROC MIXED procedure.

Sample SAS statements follow:

```
ods output LSmeans=estimates;
ods output Diffs=lsdiffs;
Proc Mixed Data=ldl_data;
  Class treatment visit_day subject_id statiny;
  Model percent_change = treatment|visit_day statiny
base_value/DDFM=KR;
repeated visit_day/type=UN subject=subject_id;
LSMeans treatment*visit_day/cl pdiff=control('0' '510');
run;
```

(where ('0' '510') is the value of the placebo ['0'] at day 510 ['510'] in interaction term treatment*visit_day)

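### The exploratory responder endpoint (any LDL-C reduction at any visit) would count most placebo subjects by chance, and its odds ratio sits at an unstable ceiling; Day 510 is a better basis

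*SAP*

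**What the plan says.** SAP 6.4.6.3 lists as exploratory "Proportion of subjects in each group with any LDL-C reduction from baseline at any visit (responders". SAP section 8 discloses it as an addition to the protocol. The any-visit count is given by arm, and then "The odds ratio and 95% confidence interval for the odds ratio will be provided using a logistic regression model". The same paragraph adds: "The number and percentage of subjects with any LDL-C reduction will also be summarized at each visit".

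Four other provisions determine how the rule behaves:

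- **Number of samples.** In SAP Table 1 (section 2.4) the row "Fasted lipid profile/biomarkers" is marked after baseline at Days 90, 150, 270, 330, 450, 510 and 540, and not at Day 30. That makes seven. SAP Appendix 1 names six for the repeated-measures model: "The visits will include Days 90, 150, 270, 330, 450, and 510, with Day 510 as the primary time-point".
- **Baseline.** SAP 6.3.3 uses a single value where several exist: "the latest assessment will be considered the 'Baseline' evaluation for analysis".
- **Missing data.** SAP 6.3.4.1 states that, unless otherwise specified, "missing data for all parameters not listed in the primary and key secondary endpoints will not be imputed". This endpoint is neither primary nor key secondary.
- **Effect size.** SAP 6.1 assumes that the difference between arms in change in LDL-C "will be no less than 30 mg/dL, with a standard deviation of 20 mg/dL".

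The plan does not state what proportion of placebo subjects it expects to meet the definition.

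**The concern.** A responder rule is normally read as the share of patients in whom the drug works. This rule compares the lowest of up to seven later values with one earlier value, and any shortfall counts, however small. LDL-C varies from visit to visit, so the lowest of several values will usually lie below a single earlier value even when nothing has changed.

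Three things follow. The placebo percentage will be high for reasons unrelated to treatment. The inclisiran percentage will be close to 100%, so the odds ratio rests on very few subjects. The chance of qualifying also depends on how many samples a subject provides. At stake is how one exploratory table is read, not the trial's main inference.

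**Working it through.** **Plan's own figure.** There is no stated responder rate to reproduce. The related design figures do reproduce: 1500 × 0.95 = 1425 evaluable subjects, and 30 mg/dL with SD 20 mg/dL and 712 per arm gives power of essentially 100%, consistent with the stated figure of more than 90%.

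**Step 1: placebo rate by chance.** Let k be the number of post-baseline samples. If baseline and the k later values are exchangeable (same distribution, symmetric dependence, no drift, no ties), baseline is the lowest of k + 1 values with probability 1/(k + 1). So P(any reduction) = 1 - 1/(k + 1), whatever the SD or the shape of the distribution.

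| Samples available | Chance rate |
|---|---|
| 1 | 50% |
| 3 | 75% |
| 6 (visits listed in Appendix 1) | 85.7% |
| 7 (schedule) | 87.5% |
| 8 (one extra, unscheduled) | 88.9% |

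**Step 2: other assumptions, k = 7.** None of these inputs is in the documents, apart from the SD used for the drift rows.

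| Assumption | Chance rate |
|---|---|
| Autoregressive correlation, 0.5 to 0.95 per 30 days | 86% to 80% |
| Random walk | 79% |
| Placebo drift of +5 or +10 mg/dL | 80% or 71% |
| Placebo drift of -5 or -10 mg/dL | 93% or 96% |
| Values rounded to whole mg/dL | 86.9% |
| Seven independent changes, 1 - 0.5^7 | 99.2% |

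The last row is an outer figure, because the seven changes share one baseline and so are not independent. Selecting on screening LDL-C leaves 87.5% when baseline is the Day 1 value. If the screening value has to serve as baseline, it gives about 92% under an assumed LDL-C distribution.

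**Step 3: the two arms under the plan's effect.** Take 20 mg/dL as the SD of change with independent errors, which gives a within-subject SD of 20/√2 = 14.1 mg/dL. Apply a constant shift of 30 mg/dL on inclisiran and none on placebo. The probability of not qualifying is the integral of φ(x)·[1 - Φ(x + 30/14.1)]^k over x.

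| | Any of 7 visits | Day 510 only |
|---|---|---|
| Inclisiran rate | 99.87% | Φ(30/20) = 93.3% |
| Placebo rate | 87.5% | 50% |
| Non-responders per 750, inclisiran | 1.0 | 50.1 |
| Non-responders per 750, placebo | 93.75 | 375 |
| Odds ratio | about 107 | about 14 |

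**Step 4: precision.** SE(log OR) = √(sum of 1/cell count).

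- Any visit: √(1/1.0 + 1/749 + 1/93.75 + 1/656.25) = √1.013 ≈ 1.0.
- Day 510: √(1/50.1 + 1/699.9 + 1/375 + 1/375) = √0.0267 ≈ 0.16.

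With placebo held at 87.5% (odds of 7), 1 inclisiran non-responder gives (749/1)/7 = 107, 2 give (748/2)/7 = 53 and 3 give (747/3)/7 = 36. With none the ratio has no finite estimate. Under the Step 3 model the chance of none is (1 - 0.00133)^750 ≈ 0.37.

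**Step 5: does the odds ratio respond to a drug effect?** Yes. Against 87.5% on placebo it is 1 with no shift, and about 1.8, 3.5, 16 and 107 for shifts of 5, 10, 20 and 30 mg/dL.

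**The case against.** The strongest case against the point is that the comparison is randomized. Both arms follow the same schedule and definition, so chance reductions occur in both. Step 5 shows an odds ratio of 1 under no effect that rises with the effect. A reader might infer from the high placebo rate that the odds ratio does not measure response at all. The documents do not support that: at group level the placebo arm separates drug effect from visit-to-visit variation, provided attendance is similar in the two arms. This part of the objection stands.

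Three further readings also go too far:

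- **87.5% as a known rate.** It is not in the documents, and it needs exchangeability, seven complete visits and no drift.
- **Both arms near 100%.** About 94 placebo non-responders per 750 are expected, so only the inclisiran cell is sparse.
- **Placebo subjects as untreated.** Protocol 4.2 and 5.2.2 have subjects continue stable background lipid therapy where they take it.

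The objection also notes what the plan already provides. The same count is given at each visit. SAP 6.4.6.2 has the proportion with at least a 50% reduction, LDL-C thresholds at Day 510 and attainment of lipid targets. The endpoint lies outside the nested and Hochberg procedures, and both arms' percentages will be shown together. This stands too, and it keeps the point minor.

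It does not answer two things. The odds ratio in 6.4.6.3 is attached to the any-visit count and not to a fixed visit, and the word responder invites a reading that the count cannot bear.

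**Conclusion.** The point holds in a limited form. The rule has no threshold and no confirmation, so most placebo subjects with complete data would be labelled responders: about 87.5% under exchangeability without drift, and roughly 71% to 99% across the alternatives tried. With missed visits the figure falls to 75% for three samples and 50% for one. Neither arm's percentage can be read as the share of patients who respond.

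The odds ratio is a legitimate comparison but a poor one. It is at a ceiling, with a standard error on the log scale of about 1.0 against about 0.16 at Day 510. Those figures assume that 20 mg/dL is the SD of change, that errors are independent and that every subject has the same 30 mg/dL effect. If part of that SD reflects variation in effect between subjects, the count of inclisiran non-responders would differ.

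This is a low-priority improvement to one exploratory table.

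**What to change.** Change one sentence in SAP 6.4.6.3 so that the responder proportion and its odds ratio are based on Day 510. Since 6.3.4.1 leaves this endpoint unimputed, the sentence should also say how subjects without a Day 510 value are counted. Keep the by-visit counts. If the any-visit count is kept, report it descriptively, without the responder label or an odds ratio.

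Day 510 does not remove chance. With no threshold, half of placebo subjects still qualify under no drift, and Φ(-5/20) = 40% or Φ(-10/20) = 31% with an assumed upward drift of 5 or 10 mg/dL. What it removes is the dependence on the number of visits and most of the instability. A prespecified minimum reduction would also lower the chance rate, and the secondary endpoint of at least 50% reduction already sets one.

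Do not require a reduction at every attended visit after Day 90 instead. Under exchangeability a subject with all six of those samples would qualify by chance 1 time in 7 (14%), but a subject with only one would qualify half the time, so early dropouts would become the easier responders.

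The cost is small. The headline percentage becomes less favourable (93% in place of nearly 100% under the plan's assumptions), and the any-visit odds ratio is lost. No new data are needed.
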